8.6.6 Clinical Laboratory Evaluations

Laboratory safety assessments include complete chemistry, hematology, liver chemistry, urinalysis and other tests. Additionally, assessment also includes serum creatinine, HBsAg and Anti-HCV.

The specific clinical laboratory evaluations and additional live chemistry testing are as below in Table 4.

Chemistry	Hematology	Urinalysis
Albumin	Hematocrit	pH
Blood urea nitrogen (urea)	Hemoglobin	Specific gravity
Calcium	Red blood cell count	Protein
Chloride	Quantitative platelet count	Glucose
CO ₂		Ketones
Creatinine	WBC count with differential	Bilirubin
Glucose	(total and %)	Blood
Phosphorous	only if WBC count is abnormal:	Urobilinogen
Potassium	Neutrophils	Leukocytes
Protein	Lymphocytes	Nitrite
Sodium	Monocytes	Microscopic examination
Uric acid	Eosinophils Basophils	(if positive for blood, protein, nitrite, or leukocytes)
Liver Chemistry Panel	Other Tests	
Alanine aminotransferase	Urine specific gravity (local to guide titration)	
Alkaline phosphatase	Urine osmolality	
Aspartate aminotransferase	Urine or serum pregnancy test (female subjects)	
Bilirubin Total and Direct	Specimen for potential DNA analysis	
Glutamate dehydrogenase (GLDH)		

Abbreviations: CO_2 = carbon dioxide; WBC = white blood cell.

All laboratory data will be summarized in International System of Units (SI). Quantitative laboratory measurements reported as "< X", i.e. below the lower limit of quantification (BLQ), or "> X", i.e. above the upper limit of quantification (ULQ), will be converted to X for the purpose of quantitative summaries, but will be presented as recorded, i.e. as "< X" or "> X" in the listings.

Descriptive statistics of absolute value and change from baseline (mean, SD, median, min, and max) for clinical laboratory data will be presented for each scheduled time point. For all continuous clinical laboratory variables, a shift table comparing the baseline value (normal, low, and high) to last observation on treatment will be presented.

For categorical data, the laboratory results will be summarized using frequency and proportion at each scheduled time point.

For urinalysis, a shift table comparing the baseline value to the maximum value will be presented (using number of subjects with results of negative, trace, or positive).

Shift table from baseline to worst post-baseline value according to abnormality assessed by investigators (normal, Clinically Significant (CS) and Not Clinically Significant (NCS)) will be presented for all applicable laboratory evaluations.

Potentially clinically significant results of clinical laboratory evaluations identified using prospectively defined criteria (Table 5) will also be summarized descriptively.

Lab Test Category	PCS Criteria		
	Sodium: <132 mmol/L		
	Sodium: >149 mmol/L		
	Potassium:<2.5 mmol/L		
	Potassium: >6.5 mmol/L		
	Calcium: <1.62 mmol/L		
Chemistry	Calcium:>3.49 mmol/L		
	Uric acid:>715 μmol/L		
	Albumin: <25 g/L		
	eGFR: Decrease from baseline of ≥25%		
	Glucose: ≤2.5 mmol/L		
	Glucose:≥14.0 mmol/L		
	Leukocytes: $\leq 2.5 \times 10^9/L$		
Hematology	Leukocytes: $\geq 15.0 \ge 10^9/L$		
	Neutrophils: $\leq 1.5 \ge 10^9/L$		
	Platelets: $\leq 50.0 \ge 10^9/L$		
	Hemoglobin: Decrease from baseline of ≥ 20 g/L		
	Hematocrit: Decrease from baseline of $\geq 10\%$ (absolute change)		
Urinalysis	Glucose: ≥2+		
	RBC/HPF: >10		
	Protein: >2+		
	Ketones: > 2 +		
	Leukocytes: >10		

Table 5: Potentiall	y Clinically	ly Important	Criteria ((PCS): Laboratory
	J		(

Abbreviations: RBC=Red Blood Cell; HPF=high power field.

Individual data listings of clinical laboratory results will be presented for each subject. Values outside of the clinical laboratory's reference range (i.e., those with low or high values) will be flagged in the clinical laboratory listings.

Abnormal laboratory results will be listed separately by all subjects.

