7.3.6 Clinical Laboratory Tests

Blood and urine specimens will be collected for the clinical laboratory (hematology, clinical chemistry, and urinalysis) and pregnancy tests (all female subjects of child-bearing potential) at the timepoints specified in the study Schedule of Procedures ([Table 1](#)). Except where noted, all laboratory testing will be performed at the central laboratory, which will return results with normal ranges to the clinical sites. A confirmatory assessment through the central lab should be obtained as soon as possible for any CS abnormal laboratory parameter if deemed necessary by the Investigator. Repeat testing for abnormal liver chemistry tests is described in [Section 7.3.7.1](#). Any other repeat laboratory testing for values that are not CS should be discussed first by the Investigator with the medical monitor before such tests are ordered. All routine testing will be conducted in the morning after an overnight fasted state (minimum of 8 hours except for water). Mild elevations in serum creatinine or serum sodium are known pharmacodynamic effects of vasopressin antagonists like lixivaptan, therefore confirmatory assessments for serum creatinine and serum sodium will be at the Investigator's discretion.

Clinical laboratory parameters for analysis are presented in [Table 6](#).

Macroscopic urinalysis will be performed via dipstick. Microscopic examination is needed only if macroscopic results are positive for blood or protein.

Additional liver chemistry tests should be collected if the subject experiences liver chemistry test abnormalities of concern or has suspicious symptom or sign of liver dysfunction ([Section 7.3.7](#)).

Table 6 Clinical Laboratory Parameters

Complete Chemistry Panel	Hematology	Urinalysis
Albumin	Hematocrit	pH
Blood urea nitrogen (urea)	Hemoglobin	Specific gravity
Calcium	Red blood cell count	Protein
Chloride	Quantitative platelet count	Glucose
CO ₂	WBC count	Ketones
Creatinine	with differential (total and %) only if	Bilirubin
Glucose	WBC count is abnormal:	Blood
Phosphorous	Neutrophils	Urobilinogen
Potassium	Lymphocytes	Leukocytes
Protein	Monocytes	Nitrite
Sodium	Eosinophils	Microscopic examination (if
Uric acid	Basophils	positive for blood, protein,
		nitrite, or leukocytes)
Liver Chemistry Panel	Other Tests	
Alanine aminotransferase	Urine specific gravity (local to guide	
Alkaline phosphatase	titration)	
Aspartate aminotransferase	Urine osmolality	

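### Neutrophils are measured at scheduled visits only when the total white count is abnormal, yet the SAP sets a separate neutrophil limit and general change and shift summaries, so scheduled testing misses a low neutrophil count with an in-range white count

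*SAP*

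**What the plan says.** **Collection.** Protocol Table 6 (Section 7.3.6) lists the white count "with differential (total and %) only if" that count is abnormal. The SAP 8.6.6 laboratory table carries the same condition, "only if WBC count is abnormal". Hematology is drawn at V1, V5, V11/last titration, V17, V24/ET and V27 (Protocol Table 1, footnote h).

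**Analysis.** SAP Table 5 sets a leukocyte limit of 2.5 x 10^9/L or below and a separate neutrophil limit of 1.5 x 10^9/L or below. SAP 8.6.6 states that absolute values and "change from baseline (mean, SD, median, min, and max) for clinical laboratory data will be presented for each scheduled time point", and adds shift tables for all continuous laboratory variables. Nothing exempts tests that are run only on a trigger, and no denominator is given for the Table 5 counts.

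**Urine microscopy.** The text of Protocol Section 7.3.6 says "Microscopic examination is needed only if macroscopic results are positive for blood or protein". Table 6 in the same section, and the SAP laboratory table, also list nitrite and leukocytes as triggers. Under urinalysis, SAP Table 5 has a red-cell limit per high-power field and a leukocyte limit of more than 10 with no unit.

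**Early termination.** SAP Section 9 replaces the planned analyses with a limited set of tables plus listings. Appendix IV keeps a hematology listing but no laboratory change, shift or Table 5 criterion table.

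**The concern.** A neutrophil limit separate from the leukocyte limit earns its place by finding cases that the leukocyte limit misses. The collection rule removes part of that group, namely subjects whose total count is in range but whose neutrophil share is low. In those subjects a blank neutrophil result means only that the test was not run.

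Non-hepatic safety is a secondary objective, and the protocol synopsis promises summaries against criteria fixed in advance. A low neutrophil percentage could be read as reassurance when most samples were never tested. The change-from-baseline rows would rest on very few samples, all selected because the white count was already abnormal.

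**Working it through.** The plan has no figure of its own to reproduce here. The check compares the collection rule with the analysis rule and then sizes the gap.

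**Inputs**
- Neutrophil limit 1.5 and leukocyte limit 2.5 x 10^9/L: SAP Table 5.
- Planned number of subjects, 50: Protocol 8.1.
- Lower limit of normal for the white count: not in the documents. Assumed 4.0 x 10^9/L, range 3.5 to 4.5.
- Proportion p of white counts flagged abnormal at a visit: not in the documents. Assumed 5%, range 2.5% to 20%.

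**Step 1: where the gap lies.** The limit is met when the neutrophil share is at or below 1.5 / white count.

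| White count (x 10^9/L) | Share that meets the limit |
|---|---|
| 3.5 | 1.5/3.5 = 42.9% or less |
| 4.0 | 1.5/4.0 = 37.5% or less |
| 4.5 | 1.5/4.5 = 33.3% or less |
| 6.0 | 1.5/6.0 = 25.0% or less |

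Between 2.5 and the lower limit of normal, the white count is abnormal, a differential is run, and the neutrophil limit works as intended. Above the lower limit of normal, scheduled testing produces no neutrophil value.

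**Step 2: how many pairs a change summary would have.** SAP 8.6 restricts change analyses to subjects with both values, and SAP 7.2.2 allows no imputation of safety data. If abnormality is independent between visits, the expected number of pairs is n x p^2. If the same subjects are always abnormal, it is n x p.

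| p | Independent visits | Same subjects always abnormal |
|---|---|---|
| 2.5% | 50 x 0.025^2 = 0.03 | 50 x 0.025 = 1.25 |
| 5% | 50 x 0.05^2 = 0.125 | 50 x 0.05 = 2.5 |
| 10% | 50 x 0.10^2 = 0.5 | 50 x 0.10 = 5 |
| 20% | 50 x 0.20^2 = 2.0 | 50 x 0.20 = 10 |

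With p = 5% and independent visits, the chance of at least one pair is 1 - (1 - 0.0025)^50 = 11.8%. SAP 7.1 takes the latest available pre-dose value as baseline, so V1 can stand in for V5. The expected number then becomes 50 x (1 - 0.95^2) x 0.05 = 0.24. Real counts are correlated within a subject, so the truth lies between the two columns.

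**Step 3: the denominator.** Over the whole Safety Population, the neutrophil percentage omits cases in untested subjects and is understated. Over tested subjects only, it describes people selected for an abnormal white count. The SAP does not say which is meant.

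**Step 4: urine microscopy.** The red-cell limit is reached through a dipstick positive for blood, which triggers microscopy under both wordings, so no gap is shown there. If the leukocyte limit of more than 10 is a microscopy count, a dipstick positive only for leukocytes yields no count under the Section 7.3.6 text but does under Table 6 and the SAP. The missing unit leaves that reading as an inference.

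**The case against.** The strongest objection is that the affected tables will not be produced. SAP Section 9 records early termination with only 6 participants in the maintenance period, and Appendix IV contains no laboratory change, shift or criterion table. That stands, and it limits the effect on this study's report. It does not correct SAP 8.6.6, and the retained hematology listing carries the same gap because unmeasured values cannot be recovered.

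The second is that a conditional differential is a deliberate choice, stated consistently in both documents. That also stands. The fault is in pairing it with a neutrophil limit and unrestricted summaries.

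Three stronger readings are tempting but not supported:
- A reader might infer that low neutrophils with a normal white count cannot be detected at all. Protocol Appendix 3 lets the medical monitor request a full blood count with differential after a liver abnormality, and Section 7.3 lets the investigator add safety assessments. Both routes are event-driven, however, and SAP 8.1 sends unscheduled results to listings only.
- A reader might infer that untested subjects are counted as normal. The SAP does not say so: SAP 8.1 provides for a missing category and SAP 7.2.2 rules out imputation. What is absent is a denominator rule.
- A reader might treat glutamate dehydrogenase (GLDH) as a third instance, since the SAP 8.6.6 table puts it in the liver panel. The sentence introducing that table says that it also covers additional liver testing, and SAP 8.6.4 with Appendix III already handles GLDH separately. It has no Table 5 limit. This is a heading correction.

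**Conclusion.** The point holds for scheduled testing. A neutrophil count at or below 1.5 x 10^9/L with an in-range white count is not picked up, although the SAP sets a limit for it. The threshold share of about 33% to 43% rests on an assumed white-count lower limit of 4.5 to 3.5. How often such cases occur cannot be estimated from the documents, so the number missed is unknown. The differential change summaries would be nearly empty: roughly 0.1 to 2.5 pairs per time point at the assumed 5% abnormal rate, and 0.03 to 10 over the whole range tried.

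The microscopy trigger is a genuine contradiction within Protocol Section 7.3.6. Its consequence depends on the unstated unit of the urine leukocyte limit.

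The primary endpoint is not affected. After early termination, the effect of the differential gap on the final report is limited to the hematology listing.

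**What to change.** **Plan as written.** Choose one:
1. Report the automated differential on every scheduled hematology sample (V1, V5, V11/last titration, V17, V24/ET, V27). It uses the same tube, so the cost is a central-laboratory order change and a few incidental findings to review.
2. Keep the conditional differential, delete the neutrophil limit from SAP Table 5 and the differential from the change and shift summaries, and state that neutrophils were not routinely assessed. This costs SAP wording only.

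**Reconciliations, a line each.** Align the microscopy trigger in the Protocol Section 7.3.6 text with Table 6 and the SAP. State the unit of the urinalysis leukocyte limit in SAP Table 5. Move GLDH out of the liver-panel heading in the SAP 8.6.6 table.

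**This terminated study.** Routine testing can no longer be added. The synoptic report should say beside the hematology listing that neutrophils were not routinely measured and that a blank entry is not a normal result. This costs one sentence.

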8.6.7 Vital Signs

Vital sign assessments are performed in order to characterize basic body function. Absolute and changes from baseline in vital signs at each scheduled time point will be summarized using descriptive statistics (n, mean, SD, median, minimum, and maximum). The parameters collected are the following: systolic blood pressure (mmHg), diastolic blood pressure (mmHg), heart rate (beats/min), respiratory rate (breaths/min), body temperature (°C), weight (kg) and BMI (kg/m²). Vital signs summary will be based on safety population.

Potentially clinically significant results of vital signs (Table 6) identified using prospectively defined criteria will also be summarized descriptively.

Table 6: Potentially Clinically Important Criteria: Vital Signs

Heart Rate Decrease of ≥ 20 beats/min or ≤ 40 beats/min		
Heart Rate Increase of \geq 20 beats/min or \geq 120 beats/min		
Diastolic Blood Pressure Decrease of $\geq 20 \text{ mmHg or} \leq 50 \text{ mmHg}$		
Diastolic Blood Pressure Increase of $\geq 20 \text{ mmHg or} \geq 105 \text{ mmHg}$		
Systolic Blood Pressure Decrease of $\geq 25 \text{ mmHg or } \leq 90 \text{ mmHg}$		
Systolic Blood Pressure Increase of ≥ 25 mmHg or ≥ 180 mmHg		
Weight Decrease of $\geq 10\%$		
Weight Increase of $\geq 10\%$		

Vital sign assessments will be presented subject in a data listing for all subjects.

8.6.8 Physical Examinations

A complete physical examination will be performed during Screening Visit 1, Visit 17 and the final Maintenance/Early Termination Visit (Visit 24) and Follow-up period (Visit 27). Brief physical examination will subsequently be measured at the time points specified in study schedule of procedures (Table 3).

Complete physical examinations will include general appearance and assessment of the following systems: skin, head, ears, eyes, and throat, respiratory system, cardiovascular system, gastrointestinal system, neurologic system, blood and lymphatic systems, and the musculoskeletal system.

The incidence of abnormality in physical examination will be tabulated separately for each visit based on the safety population.

Abnormal physical examination will be presented for each subject in a data listing for all subjects.

8.6.9 Electrocardiograms (ECG)

Observed values and changes from baseline for continuous ECG parameters including heart rate, ventricular rate, PR interval, QRS duration, QT interval (uncorrected), RR interval and QT interval corrected for heart rate according to Fridericia's formula (QTcF) interval will be

summarized over each scheduled time point in terms of absolute values using descriptive statistics (n, mean, SD, median, minimum, and maximum).

Overall evaluation of ECG will be summarized using frequency counts and percentage of subjects as normal or abnormal, and the relevance of the abnormality will be summarized by CS or NCS. QTcF will be summarized using frequency and percentage for the following categories:

Subjects with the highest QTcF post-baseline value

- <450 msec
- 450-480 msec
- $\geq 480 \text{ msec}$

Subjects with the highest QTcF change value

- <30 msec
- 30-60 msec
- >60 msec

Potentially clinically important criteria (Sponsor defined)

• \geq 450 msec

In addition, a summary shift table comparing baseline interpretation (normal, abnormal - NCS, abnormal - CS) to the Investigator interpretation at each time point will also be presented.

ECG results will be listed by dose levels and subjects for all subjects. Additionally, a listing will be provided for Investigator-identified ECG abnormalities.

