4.1.2 Exclusion Criteria

Subjects meeting any of the following exclusion criteria are not eligible for study enrollment.

1. Known sensitivity or idiosyncratic reaction to any compound present in lixivaptan and related compounds.
2. Hypovolemia on physical examination at Screening.
3. Abnormal serum sodium concentration at Screening.
4. Subjects who have taken any investigational drug or used an investigational device within 30 days, or 5 half-lives, whichever is longer, prior to Screening.
5. Subjects who are taking, have taken within the 2 weeks prior to Screening, or are expected to be taking, strong or moderate CYP3A4 or CYP2C8 inhibitors or inducers including regular use of grapefruit juice, Seville oranges or St. John's wort.
6. Simvastatin at total daily doses >10 mg or amlodipine at total daily doses >5 mg.
7. Prior use of tolvaptan within the 3 months prior to Screening OR until a previously elevated ALT level has returned to $\leq 1 \times$ ULN for at least 3 months.
8. Prior use of lixivaptan or participation in a clinical study with lixivaptan within the 3 months of Screening.
9. Prior use of conivaptan, somatostatin analogs (e.g., lanreotide, pasireotide, octreotide, etc.), metformin (allowed for diabetes mellitus), nicotinamide, bardoxolone, venglustat, demeclocycline, or mTOR kinase inhibitors (e.g., everolimus, sirolimus, etc.) to treat ADPKD within the 3 months prior to Screening.
10. Requirement for chronic diuretic use.
11. History of advanced diabetes (e.g., glycosylated hemoglobin [HgbA1c] >7.5%, and/or glycosuria by dipstick, significant proteinuria [>300 mcg albumin/mg creatinine], retinopathy), other significant renal disease, transplanted kidney, recent kidney surgery within the 6 months prior to Screening (including cyst drainage or fenestration) or acute kidney injury within 6 months prior to Screening.
12. Clinically significant incontinence, overactive bladder, or urinary retention (e.g., benign prostatic hyperplasia).
13. New York Heart Association Functional Class 3 or 4 heart failure or other significant cardiac or ECG findings that could pose a safety risk to the subject.
14. Clinically significant liver disease or impairment or active chronic hepatitis at Screening.
15. Positive test results for hepatitis B surface antigen (HBsAg) or hepatitis C (HCV) antibody.

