6.5.3 Visit 27 (End of Study Visit)

Visit 27 is the last visit in this study and will occur 28±3 days after the last dose of study drug (Visit 24). The visit will be conducted in the clinic. The following procedures will be performed at Visit 27:

- Check vital signs (sitting blood pressure and heart rate)
- Perform a brief physical exam
- Perform a 12-lead ECG
- Check AEs and SAEs
- Collect and review concomitant medication information
- Process an aliquot of first morning, fasting urine for specific gravity
- Send the remaining first morning, fasting urine for U_{osm} determination
- Collect urine for urinalysis
- Collect urine sample for a urine pregnancy test in WOCBP
- Collect a blood sample for the following laboratory testing:
 - Complete chemistry panel
 - Liver chemistry panel
 - Hematology
- Contact the IRT to complete subject's participation in PA-ADPKD-303

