8.4.5 Clinical Laboratory Tests

Descriptive statistics (n, mean, standard deviation [SD], median, minimum, and maximum) for clinical laboratory data and changes from baseline will be presented for each scheduled time point.

The baseline value is the last value observed prior to first administration of study drug and any information taken after first administration of study drug is regarded as post-baseline

information. The change-from-baseline variables will be calculated as the post-baseline value minus the value at baseline. Change from baseline on continuous data will be summarized using descriptive statistics at each scheduled time point. For categorical data, change from baseline will be summarized using frequency and proportion at each scheduled timepoint.

Individual data listings of clinical laboratory results will be presented for each subject. Values outside of the clinical laboratory's reference range (i.e., those with low or high values) will be flagged in the clinical laboratory listings.

For all continuous clinical laboratory variables, a shift table comparing the baseline value (normal, low, and high) to last observation on treatment will be presented.

For urinalysis, a shift table comparing the baseline value to the maximum value will be presented (using number of subjects with results of negative, trace, or positive).

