7 STATISTICAL CONSIDERATIONS AND ANALYSIS

7.1 Derived General Variables

The below table (Table 4) provide the list of derived variables for demographic and baseline characteristics, various duration derivations, drug compliance, baseline derivations and other important derivations applicable for this study.

Variables	Formula					
Demographic characteristics						
Age at informed consent (in years)	Age = year of informed consent – year of birth					
BMI (kg/m ²)	weight (kg)/[height (m)] 2					
Derivation of Duration						
Study Duration (Days)	(Date of Last Visit – Date of informed consent) + 1					
Study day at any visit	Date of interest – date of first dose of study drug. One day is added if this difference is ≥ 0					
Adverse event duration (in days)	Event end date - Event onset date + 1.					
Duration of Exposure						
Duration of Exposure (days) in Titration Period	(Date of last administration of study drug – Date of first administration of study drug) +1, during the 6 week titration period					
Duration of Exposure (days) in Maintenance Period	(Date of last administration of study drug – Date of first administration of study drug) +1, during the 52 week maintenance period					
Treatment Compliance						
Treatment Compliance	(Total No. of capsules dispensed – Total No. of capsules returned)*50/total assigned dose*100 where, total assigned dose will be derived by sum of (AM+PM dose)*duration of this dose level for all different dosing levels					
eGFR Baseline and Fin	al Assessment Derivation (Appendix I)					
Baseline eGFR	Mean of 3 eGFR assessments (Visit 3, Visit 4 & Visit 5) obtained during the baseline period					
Final Assessment eGFR	Mean of 3 eGFR assessments (Visit 25, Visit 26 & Visit 27) obtained during the follow-up period					
Baseline Derivations						

Table 4: Derived Variables

Baseline	Latest non-missing measurement prior to first dose of study drug administration	
Change from baseline	Test Value at Post baseline value – Baseline Value	
Geometric Coefficient of Variation (CV%) for Pharmacokinetic data		
Geometric CV%	CV (%) =100× $\sqrt{\exp(\hat{\sigma}^2) - 1}$, where $\hat{\sigma}^2$ denotes the variance of the natural log-transformed values.	
	the natural log-transformed values.	

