11.4 Appendix IV: List of Tables, Listings, and Figures

List of Tables, Listings, Figures Listing 16.2.1.1 Subject Disposition All Subjects Listing 16.2.2 Protocol Deviations All Subjects Listing 16.2.4.1 Demographic Characteristics All Subjects Listing 16.2.4.2.1 Baseline Characteristics - eGFR All Subjects Listing 16.2.4.2.2 Baseline Characteristics - ALT, AST and Total Bilirubin All Subjects Listing 16.2.4.3 Medical History All Subjects Listing 16.2.4.4 Concomitant Procedures All Subjects Listing 16.2.4.5 Medical History of Autosomal Dominant Polycystic Kidney Disease (ADPKD) All Subjects Listing 16.2.4.6 Prior and Concomitant Medications All Subjects Listing 16.2.5.1 Drug Accountability Safety Population Listing 16.2.5.2 Drug Tolerability/Modification Safety Population Listing 16.2.6.1 Listing of Serum Creatinine and estimated Glomerular Filtration Rate (eGFR) All Subjects Listing 16.2.7.1.1 Liver Dysfunction Details All Subjects Listing 16.2.7.1.2 Potential Hepatic Events All Subjects Listing 16.2.7.2 Criteria for Primary and Secondary Hepatic Safety Endpoints All Subjects Listing 16.2.7.3 Adverse Events All Subjects Listing 16.2.8.1.1 Laboratory Test Results - Hematology All Subjects Listing 16.2.8.1.2.1 Laboratory Test Results - Chemistry All Subjects Listing 16.2.8.1.3 Laboratory Test Results - Liver Chemistry All Subjects Listing 16.2.8.1.4 Laboratory Test Results - Urinalysis All Subjects Listing 16.2.8.1.6 Additional Potential Hepatic Testing All Subjects Listing 16.2.9.1 Vital Signs Results All Subjects Listing 16.2.10 .1 Electrocardiogram (ECG) Results All Subjects Listing 16.2.12 Pregnancy Results All Female Subject Table 14.1.1.1 Summary of Subject Disposition All Subjects Table 14.1.1.4 Summary of Protocol Deviation Enrolled Population Table 14.1.2.1.1 Summary of Demographic Characteristics Enrolled Population Table 14.1.2.2.1 Summary of Baseline Disease Characteristics Enrolled Population Table 14.1.5.1 Summary of Study Drug Exposure Safety Population Table 14.3.1.1.1 Overall Summary of Treatment Emergent Adverse Events (TEAEs) Safety Population Table 14.3.1.2.1 Summary of TEAEs by System Organ Class and Preferred Term Safety Population Table 14.3.1.2.2.1 Summary of Serious TEAEs by System Organ Class and Preferred Term Safety Population Table 14.3.1.2.2.2 Summary of Non-serious TEAEs by System Organ Class and Preferred Term Safety Population Table 14.3.1.2.4 Summary of Adverse Event of Special Interest by System Organ Class and Preferred Term Safety Population Table 14.3.2.1 Summary of Liver Chemistry Abnormalities Defined as Primary and Secondary Hepatic Safety **Endpoints Safety Population** Table 14.3.5.4 Summary of Post-Baseline QTcF Safety Population

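### The QTcF categories overlap at 480 ms, and the ≥450 ms criterion does not separate values already present before dosing

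*SAP*

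**What the plan says.** SAP 8.6.9 has three QTcF blocks. Under "Subjects with the highest QTcF post-baseline value" the categories are <450, 450-480 and ≥480 msec. Under "Subjects with the highest QTcF change value" they are <30, 30-60 and >60 msec. Under "Potentially clinically important criteria (Sponsor defined" there is one entry, ≥450 msec. The section also plans a shift table of the investigator's ECG interpretation from baseline.

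SAP 7.1 defines baseline as "Latest non-missing measurement prior to first dose of study drug administration". For the ECG that is Visit 5, or Visit 1 if Visit 5 is missing. The schedule of procedures places later ECGs at Visits 17, 24/ET and 27 only. On timing, protocol 6.5.3 states: "Visit 27 is the last visit in this study and will occur 28±3 days after the last dose of study drug".

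SAP 8.1 and 8.6 split safety summaries by default into titration and maintenance combined, follow-up, and overall. SAP 8.1 also keeps unscheduled results out of tables.

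On entry, exclusion criterion 13 (protocol 4.1.2) covers certain heart failure classes and "other significant cardiac or ECG findings that could pose a safety risk to the subject". It gives no QTcF number.

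After early termination, SAP Appendix IV keeps "Table 14.3.5.4 Summary of Post-Baseline QTcF Safety Population" and ECG Listing 16.2.10.1. The ECG shift table is not on that list.

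**The concern.** There are two separate defects.

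- **Overlap.** The middle and upper value categories share 480 ms, so they are not mutually exclusive.
- **No baseline condition.** The ≥450 ms criterion counts a level, whether it arose on drug or was there before. Other criteria in the SAP do look at baseline: Table 5 flags eGFR, hemoglobin and hematocrit on a decrease from baseline.

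In a single-arm study there is no control group against which to read a count of subjects at ≥450 ms, so the baseline split is the only internal reference. The planned shift table would have given a coarse version of it, on the investigator's interpretation, but it was dropped. What is at stake is how one descriptive cardiac table reads in the synoptic report.

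**Working it through.** The plan states no QTcF rate, mean or SD, so there is no figure to reproduce. The first three steps are logic checks; the fourth only illustrates size.

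**1. Boundaries as written.** 449 falls in <450; 450 and 479 fall in 450-480; 480 falls in both 450-480 and ≥480; 481 falls in ≥480 only. The change categories are clean: 30 and 60 each fall only in 30-60. With 6 subjects, one of them at exactly 480 ms, the value categories would total 7/6 = 116.7%.

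**2. Can the change categories recover baseline status?** Take two subjects whose highest post-baseline value is 455 ms.

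- Subject A, baseline 455: change 455 − 455 = 0.
- Subject B, baseline 449: change 455 − 449 = 6.

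Both are counted in 450-480, at ≥450 ms, and in change <30. Only B newly crossed 450 ms. Separate marginal counts cannot tell A from B; a cross-tabulation against baseline can. The title of Table 14.3.5.4 also does not show whether the change categories are kept.

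**3. Where Visit 27 goes.** SAP 8.6.9 names no visits and gives no on-treatment window. Protocol 8.4.5, on laboratory data, says "any information taken after first administration of study drug is regarded as post-baseline", with no end-of-treatment cut-off. With the default split, Visits 17 and 24/ET fall under titration and maintenance, and Visit 27 under follow-up. The overall column is the only one that takes a maximum across both. Visit 27 is one of three scheduled post-baseline ECGs for a completer, and one of two for a subject who stops before Visit 17.

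**4. Illustrative size, no drug effect.** Each QTcF is a subject mean, drawn from N(m, s_b²), plus visit error from N(0, s_w²), rounded to 1 ms. There is one baseline and three post-baseline ECGs, in 400,000 simulated subjects. The values of m, s_b and s_w are assumptions, not taken from the documents.

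| m / s_b / s_w (ms) | ≥450 at V17, V24 or V27 | ≥450 at V17 or V24 | ≥450 at V17 or V24, baseline <450 |
|---|---|---|---|
| 410/15/8 | 2.1% | 1.6% | 1.1% |
| 410/20/10 | 7.4% | 6.0% | 3.5% |
| 420/15/8 | 8.0% | 6.4% | 3.9% |
| 420/20/10 | 16.3% | 13.6% | 6.9% |
| 430/15/8 | 21.5% | 18.0% | 9.0% |
| 430/20/10 | 30.3% | 26.2% | 11.0% |

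- **On-treatment column.** The share of flagged subjects already at ≥450 ms at baseline runs from 1 − 1.1/1.6 ≈ 31% to 1 − 11.0/26.2 ≈ 58%.
- **Overall column.** 14% to 23% of flagged subjects qualify on Visit 27 alone.
- **Overlap.** A maximum of exactly 480 ms occurs in at most 0.3% of subjects.
- **Scaled to 6 subjects.** The on-treatment count is 6 × 0.016 = 0.10 to 6 × 0.262 = 1.57. With baseline <450 ms it is 6 × 0.011 = 0.07 to 6 × 0.110 = 0.66.

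The scaling assumes that all 6 have both on-drug ECGs. SAP 9 says that most terminated prematurely, and Visit 17 is 24 weeks into maintenance (six 4-week intervals), so it probably overstates the counts.

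**The case against.** The case on the other side is substantial.

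- **Visit 27.** A reader might infer that the retained table counts off-drug ECGs as on-drug. The documents do not support this. The default split already gives follow-up its own column, SAP 8.6.9 does not override it, and the table shells are in a separate document. What stands is that the overall column can mix the two.
- **Entry.** A reader might infer that ECG entry is unrestricted. Exclusion 13 applies; only a numeric QTcF limit is missing.
- **Any post-baseline value.** Unscheduled ECGs are listed, not tabulated, so only scheduled values can count.
- **Attribution.** A reader might infer that the table attributes pre-existing abnormality to lixivaptan. It is a descriptive count with no causal claim, and SAP 8.6 plans no hypothesis testing.
- **Recoverability.** The change categories are baseline-adjusted, and Listing 16.2.10.1 shows each subject's ECGs. This is right for the listing. The change categories fail to link the two counts, as step 2 shows.
- **Scale.** With 6 maintenance subjects, a cross-tabulation adds little to a synoptic report, and a large simulation does not describe this study. Both points stand and limit the weight of the concern.

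**Conclusion.** The concern holds in a limited form. The 480 ms overlap is a plain drafting error with almost no numerical effect. The missing baseline condition is the more useful point: the only retained ECG summary table can count subjects who were at ≥450 ms before dosing, and nothing else in the tables identifies them. The two defects are independent; the overlap causes double counting, not the counting of pre-existing or off-drug values.

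The impact is small. The table is descriptive, 6 subjects entered maintenance, and individual ECGs are listed. The size of the Safety Population on which the table is based is not given. The rates above depend on the assumed means and SDs and should be read as illustration only. The statement about Visit 27 rests on the default period split being applied to this table.

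**What to change.** In SAP 8.6.9 and the shell for Table 14.3.5.4:

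1. Make the value categories exclusive: <450, 450 to <480, ≥480 ms.
2. In the titration and maintenance column, cross-tabulate the highest scheduled QTcF against baseline category (<450 or ≥450 ms). Report new-onset ≥450 ms with subjects below 450 ms at baseline as the denominator.
3. Keep Visit 27 in the follow-up column and out of the on-treatment maximum. If an overall column is kept, label it as including follow-up.

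The cost is SAP and table-shell wording plus minor programming. No new data are needed, because the Visit 5 (or Visit 1) ECG is already collected.
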